On the day of the operation, the allocation was confirmed, and appropriate consent was obtained for the given surgical procedures. Vaginal hysterectomy and laparoscopic hysteropexy were combined with anterior and/or posterior repair at the surgeon's discretion at the time of the operation. Each participant was initially followed-up with in the clinic at one week, one month, three months, and one year post-surgery as part of departmental procedure. Postoperative pain scores were evaluated 24 hours after surgery by a visual analog scale (VAS) score. Uterovaginal prolapse was assessed again using the International Consultation on Incontinence Questionnaire Vaginal Symptoms (ICIQ-VS) questionnaire and the Pelvic Organ Prolapse Quantification (POP-Q) system by another researcher, and then the operator. During interviews, further questions were asked regarding postoperative recovery, current urinary symptoms, and satisfaction with the operation. Subjective surgical outcome was measured using the Patient Global Impression of Improvement (PGI-I), which is a validated global index of response to prolapse surgery consisting of a seven-point scale upon which patients may compare their preoperative and postoperative conditions (with 1 being "very much better" and 7 being "very much worse").^[9] The PGI-I scale was evaluated one year after surgery with each of the patients.

The participants' prolapse symptoms, and their impacts, were evaluated both before and one year after surgical treatment. A subjective assessment of the prolapse was made using the ICIQ-VS.^[10] Objective assessment of pelvic organ prolapse was performed during a Valsalva maneuver using a Sims' speculum, and the frequently-used POP-Q scale was evaluated.^[11] Patients were also asked to complete the Urogenital Distress Inventory Short Form (UDI-6) and the Incontinence Impact Questionnaire Short Form (IIQ-7). The UDI-6 and IIQ-7 are accepted as validated questionnaires that are useful in the assessment of urogenital symptoms and disease-specific quality of life.^[12]

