The measure for the primary outcome was treatment failure, defined as recurrent apical prolapse that required surgery within the first year after initial surgery. The secondary outcome measures were changed in anatomy quantified by POP-Q and symptoms quantified using the ICIQ-VS questionnaire scores for prolapse, quality of life, and PGI-I, UDI-6, IIQ-7 scores. Other secondary outcome measures were operation time, pain score, blood loss, and postoperative hospital stay.

Statistical analysis

Data analysis was performed with SPSS (version 20.0; Chicago, IL). Data were analyzed using descriptive statistical methods (mean, standard deviation, median, frequency, rate, minimum, and maximum). One sample Kolmogorov–Smirnov test was performed to analyze the distribution of the data. For group comparisons of parameters with quantitative data showing normal distribution, Student's t-test was used, while a Mann–Whitney U test was used for comparing other parameters not showing normal distribution. A p value of less than .05 was considered statistically significant.

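### The secondary one-year scores are compared by two-sample tests that by default drop women without a one-year value, do not adjust for the pre-operative score, and have no missing-data method behind them

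*Combined protocol and SAP*

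**What the plan says.** Follow-up in the Materials and Methods is departmental routine: "Each participant was initially followed-up with in the clinic at one week, one month, three months, and one year post-surgery". That fixes when women are seen, not what is measured at each visit.

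- Prolapse symptoms and their impacts "were evaluated both before and one year after surgical treatment".
- For the repeat examination the text says "Uterovaginal prolapse was assessed again using the International Consultation on Incontinence Questionnaire Vaginal Symptoms (ICIQ-VS) questionnaire and the Pelvic Organ Prolapse Quantification (POP-Q) system", without naming a visit.
- For the global impression of improvement: "The PGI-I scale was evaluated one year after surgery with each of the patients".

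These scores are secondary: "The secondary outcome measures were changed in anatomy quantified by POP-Q and symptoms quantified using the ICIQ-VS questionnaire scores", with quality of life, PGI-I, UDI-6 and IIQ-7 added. The primary outcome is different, namely "recurrent apical prolapse that required surgery within the first year after initial surgery", and this point does not concern it.

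The Statistical analysis section compares normally distributed quantitative data by Student's t-test, while Mann-Whitney "was used for comparing other parameters not showing normal distribution". It names no covariate, repeated-measures model, analysis population, missing-data method or sensitivity analysis.

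**The concern.** A two-sample test on the one-year value, or on change from baseline, needs a one-year value from every woman it counts. A woman who does not return drops out of the comparison, whatever is known about her from before surgery or from earlier visits.

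The one-year visit comes nine months after the previous one. The women know which operation they had, because the allocation was confirmed and consent for that procedure taken on the day. One operation keeps the uterus with mesh and the other removes it, so reasons for not returning could differ by arm.

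If repeat surgery turns out to be uncommon (an assumption; the documents give no rate), these scores will carry most of the evidence on benefit. A comparison distorted by who came back could then suggest a difference that is not there or hide a real one. The planned analysis offers no check on this. It also gives up the precision available from the pre-operative score, which is collected anyway.

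**Working it through.** The text gives no sample size, SD, effect size or attendance, so there is no planned figure to reproduce. What follows is an illustration.

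**Assumed inputs.** 30 women per arm; no true difference; scores in SD units and normal. Correlation of the one-year score is 0.6 with the three-month state and 0.3 with baseline; baseline and three-month correlate 0.3. Absence is logistic, with log-odds of 1 per SD. Simulations used 6000 trials per scenario.

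**Step 1: bias of the available-case difference.** With 20% absent, the mean of the variable driving absence shifts by about 0.17 SD among those who attend. If the driver is the three-month state, the one-year mean shifts by correlation × 0.17.
- One arm affected: 0.6 × 0.17 = 0.10 SD.
- Opposite directions: 2 × 0.6 × 0.17 = 0.20 SD.
- Same mechanism and rate in both arms: the shifts cancel, giving about 0.

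**Step 2: false-positive rate.** With 24 women left per arm, the standard error is √(2/24) = 0.289. For opposite directions, 0.204/0.289 = 0.71, and Φ(−1.96 + 0.71) + Φ(−1.96 − 0.71) = 0.106 + 0.004 = 11%. For one arm, 0.102/0.289 = 0.35, giving 0.054 + 0.010 = 6.4%.

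Simulation agrees:

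| Absence, driven by three-month state | Bias (SD) | False positives |
|---|---|---|
| 20%, same mechanism in both arms | about 0 | about 5% |
| 20%, one arm affected | 0.10 | 6% to 7% |
| 5%, opposite directions | 0.055 | 5.7% |
| 10%, opposite directions | 0.11 | about 7% |
| 20%, opposite directions | 0.20 to 0.21 | about 11% |
| 25%, opposite directions | 0.25 to 0.26 | 13% to 14% |

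With 50 per arm (20%, opposite directions) the bias is 0.21 SD and false positives are about 16%. Unequal rates alone (20% against 10%, same slope) give 0.04 to 0.06 SD at a three-month correlation of 0.5 to 0.7.

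**Step 3: what adjustment recovers.** Bias in SD units, 20% absent:

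| Driver of absence | Available case | Baseline only | Baseline and three-month |
|---|---|---|---|
| Three-month state, opposite directions | 0.21 | 0.18 | about 0 |
| One-year state, one arm | 0.17 | 0.16 | 0.11 |
| One-year state, opposite directions | 0.35 | 0.32 | 0.23 to 0.24 |

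The zero in the first row is built in, because absence was generated from the same score the model conditions on. Across three-month correlations of 0.5 to 0.7, baseline alone removes about 7% to 18% of the bias.

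**Step 4: precision.** Adjusting for a baseline correlated 0.3 multiplies the standard error by √(1 − 0.3²) = 0.954 in large samples. At this size the gain is about 3% to 4%. An unadjusted test of change would be worse than the one-year value alone: its SD is √(2 × (1 − 0.3)) = 1.18 times as large.

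**The case against.** The strongest reply is that the plan cannot be faulted for leaving aside three-month data it does not describe. A reader might infer from the visit schedule that three-month scores exist for every woman and would correct the problem. The documents do not support this. Symptom scores are placed before surgery and at one year, the repeat ICIQ-VS and POP-Q assessment is tied to no visit, and a scheduled visit is not an attended one. This part of the reply stands.

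It also stands that outcome-related absence alone does not bias the contrast. It has to differ between arms, and opposite directions is a severe case. The text may even suggest complete follow-up, since it speaks of each patient at one year. But that wording gives no count, and the flow diagram that would show losses is not in the available text. If follow-up was complete, the bias concern falls away and only the modest gain in precision remains.

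Timing limits the remedy. Admissions ran from June 2017 to January 2019 and the document is dated 10 January 2020, so if surgery followed promptly, nearly all three-month visits are past.

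Finally, the illustration uses normal data and the t-test. The same selection affects Mann-Whitney, but its size there was not computed.

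None of this answers the remaining point: the plan states no way of handling missing one-year scores and does not adjust for a baseline it collects.

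**Conclusion.** The point holds in limited form, for secondary outcomes only. The named tests by default compare only women with a one-year value and do not adjust for the pre-operative score. Nothing is said about missing values. Restriction to available cases is inferred from the tests named; the plan does not state it.

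The arm difference can be biased if absence differs between arms. At an assumed 20% absent this is about 0.10 SD with one arm affected and 0.20 SD with opposite mechanisms (false positives about 6% to 7% and 11% with 30 per arm), and about 0 with the same mechanism. Arm size, attendance, correlations and slopes are all assumptions.

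Two stronger readings should be avoided. One is that the comparison is biased: neither the amount nor the pattern of absence is known. The other is that a better model would cure it: baseline alone removes little, and even three-month scores leave 0.11 of 0.17 SD (one arm) if absence depends on one-year status. The change is worth making because it is cheap, rests on a weaker assumption than the planned tests, and is somewhat more precise even with complete data. Confidence is medium.

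**What to change.** 1. For ICIQ-VS, POP-Q measurements, UDI-6 and IIQ-7, replace the two-sample tests by a regression of the one-year score on arm and the baseline value.
2. State at which visits each score was taken. For any score recorded at three months, extend the model to repeated measures: three-month and one-year values as outcomes; baseline, arm, visit and arm-by-visit as terms; unstructured covariance. If any women have not yet reached that visit, take the three self-completed forms there.
3. Report the one-year arm difference with its 95% CI, and the number with a one-year score in each arm.
4. Add one sensitivity analysis that shifts the missing values in one arm by a fixed amount set in advance.
5. Leave PGI-I outside the model, since it has no earlier value; report the number scored by arm.

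The cost is a few lines of analysis plan, a model that SPSS provides, and at most three short forms at an existing visit. The downside is that the model assumes absence is explained by the observed scores. It removes only part of the bias if absence depends on one-year status or if only baseline scores exist, which is why items 3 and 4 are needed.

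### A Kolmogorov–Smirnov screen of the trial data, with no Lilliefors correction stated, chooses the test for each quantitative secondary outcome; name one method per outcome instead

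*Combined protocol and SAP*

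**What the plan says.** The Statistical analysis section of the combined protocol and SAP sets out a two-step rule. First, "One sample Kolmogorov–Smirnov test was performed to analyze the distribution of the data". Then, "For group comparisons of parameters with quantitative data showing normal distribution", the t-test applies, and "a Mann–Whitney U test was used for comparing other parameters not showing normal distribution". The threshold is given once: "A p value of less than .05 was considered statistically significant".

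The section names the software ("Data analysis was performed with SPSS (version 20.0; Chicago, IL") but not the procedure used for the screen. It does not say:

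- where the reference mean and SD came from;
- whether a Lilliefors correction was applied;
- whether the screen ran on pooled data or on each arm;
- what cut-off counted as normal;
- which outcome took which branch.

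The paragraph just before it lists the outcomes. The primary outcome is "treatment failure, defined as recurrent apical prolapse that required surgery within the first year after initial surgery", a yes/no event that this rule does not reach. The secondary outcomes are POP-Q, ICIQ-VS, quality of life, PGI-I, UDI-6 and IIQ-7, and then: "Other secondary outcome measures were operation time, pain score, blood loss, and postoperative hospital stay". The document states no sample size.

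**The concern.** Two things are wrong with the rule, and they differ in how certain they are.

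The first needs no assumption. The test behind each secondary p-value is chosen by looking at the trial data. The two tests do not address the same quantity: one compares means, the other rank ordering. What is being compared for blood loss or hospital stay is therefore unknown until the screen has run.

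The second is conditional. The one-sample Kolmogorov–Smirnov p-value is valid for a normal curve fixed in advance. When the curve is fitted to the same sample, it lies closer to the data than a fixed curve would, the distance statistic is too small, and the standard critical value is too lenient. The Lilliefors correction exists to repair this. The plan cites no external mean or SD and no correction, so the uncorrected version is the natural reading. On that reading the screen tends to pass moderately skewed outcomes as normal.

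At stake are some efficiency on skewed outcomes and a fixed, reportable quantity for each secondary comparison.

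**Working it through.** The plan gives no figure to reproduce, so the check is by simulation. The rule and the 0.05 threshold come from the Statistical analysis section. Everything else is assumed: sample sizes (20 to 100 values entering the screen, 15 to 50 per arm, 1:1), distributions, two-sided tests, and 0.05 as the screen's cut-off. Runs use 10,000 replicates unless noted.

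**Step 1: the screen on normal data.** The statistic is D = max over x of |Fₙ(x) − Φ((x − m)/s)|, where Fₙ is the empirical distribution and m and s are the sample mean and SD. Compared with the ordinary one-sample 5% critical value, D leads to rejection of normal data in about 0.05% of samples or fewer. The nominal rate is 5%.

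**Step 2: the screen on skewed data.** Lognormal data with log-SD 0.6 are rejected in 8% (n=30), 14 to 15% (n=40) and 23% (n=50) of samples. Between 100 − 23 = 77% and 100 − 8 = 92% therefore pass as normal. The share judged normal in other settings is:

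| Assumed data | n | Uncorrected | Lilliefors |
|---|---|---|---|
| Gamma, skew 1 | 40 | 99% | 67% |
| Gamma, skew 1 | 100 | 93% | 29% |
| Lognormal, skew 1.75 (log-SD 0.5) | 40 | 94% | 40% |
| Lognormal, skew 1.75 (log-SD 0.5) | 100 | 60% | 5% |
| Exponential, skew 2 | 40 | 79% | 10% |
| Exponential, skew 2 | 100 | 8% | 0% |
| Lognormal, skew 6.2 | 40 | 39% | 2% |
| Hospital stay in whole days | 20 | 68% | 4% |
| Hospital stay in whole days | 40 | 7% | 0% |
| Skewed seven-point score | 20 | 40% | 0.2% |
| Skewed seven-point score | 40 | 0.1% | 0% |

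The screen is weak against mild to moderate continuous skew. It is not weak against strong skew or coarse scores, or once samples are larger.

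**Step 3: pooled or per arm.** The plan leaves this open, and it matters. Take 40 per arm and log-SD 0.6. If Mann–Whitney is used when either arm fails, a 14 to 15% rejection rate per arm gives 1 − 0.86² = 26% to 1 − 0.85² = 28% of trials sent to Mann–Whitney (simulated: 27%). A screen on the pooled 80 values sends 57%.

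**Step 4: type I error.** Over the simulated distributions and 15 to 50 per arm, the two-step rule had type I error 0.042 to 0.055 (pooled screen) and 0.040 to 0.061 (per-arm screen). Tests fixed in advance gave 0.034 to 0.055 (t) and 0.041 to 0.053 (Mann–Whitney). The screen is not needed to protect the error rate.

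**Step 5: power.** With 40 per arm, log-SD 0.6 and a shift giving the log-scale t-test about 80% power, two separate simulations gave:

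| Simulation | t | Gated rule | Mann–Whitney | t on logs |
|---|---|---|---|---|
| A | 72% | 75% | 77% | 79% |
| B | 74% | 77% | 78% | 80% |

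The gated rule is 79 − 75 = 4 or 80 − 77 = 3 points below the log-scale test, and 77 − 75 = 2 or 78 − 77 = 1 below Mann–Whitney. Over the settings tried, the shortfall against the log-scale test is about 1 to 4 points.

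**Step 6: does the verdict change?** Share of trials in which significance differs (40 per arm, same power setting, 4,000 runs):

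| log-SD | t vs Mann–Whitney | Gated (per arm) vs Mann–Whitney | Gated (pooled) vs Mann–Whitney |
|---|---|---|---|
| 0.5 | 11% | 8.1% | 6.5% |
| 0.6 | 13% | 7.3% | 5.0% |
| 0.75 | 16% | 5.1% | 2.1% |
| 0.9 | 21% | 2.7% | 0.5% |

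The last two columns measure what the screen does. Where the two fixed tests differ most, the screen usually selects Mann–Whitney, so the gated result seldom departs from it.

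**The case against.** The strongest reply is that this is a common reporting sentence with little practical effect. The error rate is held, the power loss is a few points at most, the primary outcome is untouched, and the missing correction may be only a missing word. All of that stands, and it limits the weight of the point. It does not defend the rule, because either test fixed in advance performs at least as acceptably without the screen.

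Four stronger readings are tempting, and the documents do not support them.

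- *The screen is invalid.* That depends on mean and SD having been estimated without correction. The section does not say so; the SPSS procedure is not named.
- *It passes most skewed outcomes as normal.* This holds only for mild to moderate continuous skew at about 30 to 50 values. In the assumed scenarios at n=40, hospital stay in whole days passes in 7% of samples and a skewed seven-point score (the PGI-I format) in 0.1%. A pooled screen at 40 per arm with log-SD 0.6 passes only 100 − 57 = 43%.
- *The verdict often turns on the screen.* The 11 to 21% in Step 6 compares two fixed tests and does not measure the screen. The relevant figure is about 0.5 to 8%.
- *Results were selected after seeing both p-values.* Nothing in the document indicates this. If it were done, counting a result as significant when either test reached 5% would give a type I error of about 0.054 to 0.073 in the same simulations.

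It is also fair to say that which method goes with which outcome is partly preference. The necessary change is that one is named.

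**Conclusion.** The concern holds in a limited form. That the trial data choose the test for each quantitative secondary outcome is plain from the text. That the screen is badly calibrated is conditional on estimated parameters and no correction. The size of its blind spot also depends on sample sizes and distributions that had to be assumed.

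The damage to inference is small and does not reach the primary outcome. What remains is a small, avoidable loss of power and a secondary analysis in which no outcome has a fixed test or a fixed quantity of interest. This is a cheap improvement, not a threat to the trial's main conclusion.

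**What to change.** Delete the Kolmogorov–Smirnov step and name one method for each secondary outcome, to be used whatever a normality test would show. One workable allocation:

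- **Blood loss, operation time, hospital stay, VAS pain, PGI-I and POP-Q stage:** Mann–Whitney, with the Hodges–Lehmann shift and its 95% CI. A log-scale comparison, reported as a ratio of geometric means with 95% CI, is an acceptable alternative for operation time, and for blood loss if all values are positive.
- **ICIQ-VS, UDI-6 and IIQ-7:** mean difference with 95% CI.

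If the analysis has already been done, which the section's past tense suggests, report both tests for every quantitative secondary outcome and label the choice between them as data-driven. Also state how the screen was run: corrected or not, pooled or per arm.

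The cost is one paragraph of wording and a little re-analysis, with no new data. The downside is a slightly less efficient test for any outcome assigned to ranks that proves close to normal.

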Document Date: 10.01.2020

NCT: NCT03436147

Vaginal-assisted laparoscopic sacrohysteropexy (VALH) and vaginal hysterectomy+vaginal vault suspension (VH+VVS) for advanced uterine prolapse: 12month preliminary results of a randomized controlled study Materials and Methods

In this study, the first-year results of a single-center, randomized controlled study of two parallel groups, conducted in the tertiary referral training and research hospital, were evaluated. The study included women who were admitted to our urogynecology unit for stage 2–4 symptomatic uterine prolapse between June 2017 and January 2019. The study was approved by our hospital's local ethics committee (approval number: 2018/23).

Requirements for participation were that the women be over 18 years of age with no desire to preserve fertility (subjects had completed childbearing or were practicing reliable contraception), have a normal size uterus (< 10 cm) on examination or ultrasound, and agree to participate in principle. They were then given further information about the trial, and consent was sought either in an outpatient clinic or at the next visit for preoperative assessment. Exclusion criteria were: cervical elongation (surgeon's discretion), prior prolapse surgery, current foreign-body complications, increased risk or recent history of cervical dysplasia, chronic pelvic pain, significant uterine abnormalities, abnormal menstruation or postmenopausal bleeding within the previous 12 months, and a significantly enlarged fibroid uterus or concomitant medical problems precluding general anesthesia or the assumption of a steep Trendelenburg position. Written informed consent was obtained from all of the participants.

Participants were randomly assigned to either of two groups: Group A (VALH) or Group B (VH+VVS). The consolidated standard of reporting trials (CONSORT) flow study diagram is presented in Figure 1. Simple randomization was performed by the distribution of blind envelopes in order to separate the patients into the groups; this randomization was performed before admission to surgery. Those who subsequently had a strong preference for either operation and consequently declined to continue in the study were excluded and not put through the randomization process.

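### POP-Q and ICIQ-VS are measured before surgery and at one year, but the group tests do not use the preoperative value as a covariate, and the quantity tested is not named

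*Combined protocol and SAP*

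**What the plan says.** Materials and Methods, in the paragraph on assessment, states: "The participants' prolapse symptoms, and their impacts, were evaluated both before and one year after surgical treatment". It then names ICIQ-VS for the subjective and POP-Q for the objective assessment. The preceding paragraph says that both instruments were applied again after surgery, so preoperative values exist for these two.

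For the urinary questionnaires the text reads "Patients were also asked to complete the Urogenital Distress Inventory Short Form (UDI-6) and the Incontinence Impact Questionnaire Short Form (IIQ-7"; that sentence gives no time point. PGI-I has no baseline by construction: "The PGI-I scale was evaluated one year after surgery with each of the patients".

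The outcome paragraph just above Statistical analysis reads: "The secondary outcome measures were changed in anatomy quantified by POP-Q and symptoms quantified using the ICIQ-VS questionnaire scores". UDI-6 and IIQ-7 scores follow in the same list.

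Statistical analysis names two tests for comparing the groups. One is Student's t: "For group comparisons of parameters with quantitative data showing normal distribution, Student's t-test was used". The other is the rank test: "a Mann–Whitney U test was used for comparing other parameters not showing normal distribution". A one-sample Kolmogorov–Smirnov test examines the distribution. No covariate, regression model or paired analysis is mentioned, and the section does not state which quantity enters the tests.

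**The concern.** A woman's preoperative score often predicts her one-year score. Where it does, a comparison that ignores it leaves explainable variation in the error term. Randomisation was simple and no stratification on baseline severity is described, so nothing in the design limits chance imbalance in the preoperative scores.

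The unnamed quantity adds to this. A test on the one-year value and a test on change are both valid under randomisation, but they differ in precision and respond to a chance baseline imbalance in opposite directions. A reader cannot interpret a p-value for POP-Q or ICIQ-VS without knowing which was used.

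The point covers POP-Q and ICIQ-VS, and UDI-6 and IIQ-7 only if a preoperative score was taken. It does not touch PGI-I, operation time, pain score, blood loss, hospital stay or the binary primary outcome.

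**Working it through.** **Inputs.** From the documents: a 0.05 significance level, the two tests, and measurement of POP-Q and ICIQ-VS before surgery and at one year. Sidedness, allocation ratio, arm size, SD, effect and before–after correlation (ρ) are not given, and there is no power figure to reproduce. Assumed for illustration: two-sided testing, 1:1 allocation, n = 30 per arm, a difference of 0.5 one-year SDs, equal SDs before and after, normal data, and ρ of 0.2, 0.5 and 0.7.

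**Variance of the group comparison, relative to the one-year value alone**
- One-year value: 1.
- Change: 2(1 − ρ) = 1.6, 1.0, 0.6.
- ANCOVA in large samples: 1 − ρ² = 0.96, 0.75, 0.51.
- ANCOVA allowing for estimation of the slope: (1 − ρ²)(1 + 1/(2n − 4)). With n = 30 the second factor is 1 + 1/56 = 1.0179, giving 0.977, 0.763, 0.519.

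**Power.** The noncentrality is 0.5 × √(n/2) ÷ √(relative variance), with √(30/2) = 3.873. Degrees of freedom are 58 for the t-tests and 57 for ANCOVA.

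| ρ | One-year t-test | Change t-test | ANCOVA |
|---|---|---|---|
| 0.2 | ncp 1.936, 47.8% | ncp 1.531, 32.5% | ncp 1.959, 48.6% |
| 0.5 | ncp 1.936, 47.8% | ncp 1.936, 47.8% | ncp 2.216, 58.7% |
| 0.7 | ncp 1.936, 47.8% | ncp 2.500, 69.1% | ncp 2.688, 75.2% |

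**Worst case for adjustment.** At ρ = 0, ANCOVA has 47.1% against 47.8% for the one-year t-test, a loss of 0.7 points. At 15 per arm the corresponding figures are 25.4% and 26.2%; at 50 per arm, 69.2% and 69.7%. The loss is under 1 point in each case.

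**Unequal SDs.** The variance for change becomes 1 + k² − 2ρk, where k is the baseline SD divided by the one-year SD. At ρ = 0.5 and 30 per arm, k = 0.5 gives 59.4% for change and k = 2 gives 19.6%, against 58.7% for ANCOVA. So a change score can match ANCOVA, or fall well behind it, depending on a ratio that the documents do not give.

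**Chance imbalance.** Suppose the arms differ by 0.3 SD at baseline. The one-year comparison shifts by 0.3ρ = 0.06, 0.15, 0.21 SD. The change comparison shifts by −0.3(1 − ρ) = −0.24, −0.15, −0.09 SD. ANCOVA corrects for the imbalance under the linear model.

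**Skewed scores.** Linear ANCOVA should not replace Mann–Whitney here. In a simulated lognormal case (log-SD 0.8, 0.5 SD shift, 30 per arm, ρ = 0.5 on the underlying normal scale), power was 88% for Mann–Whitney on the one-year value, 94% for rank-based ANCOVA and 62% for linear ANCOVA.

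**The case against.** Three objections carry weight.

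*Baseline may already be in use.* A reader might infer that the preoperative data are ignored altogether. The documents do not support that. The outcome wording suggests change for POP-Q and can be read as covering symptoms too, and a t or Mann–Whitney test on change uses baseline by subtraction. What can be said is that baseline is not a covariate and that its use through a change score is unclear.

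*No inflated error rate is shown.* A reader might also infer a false-positive rate above 5%. In simulation at 30 per arm (ρ 0.2 to 0.7, baseline SD 0.5 to 2 times the one-year SD), counting a score as significant if either the one-year or the change test is significant gives about 7 to 10%. That applies only if both were tested and either could be reported, and nothing in the documents describes this. Naming the quantity removes the possibility without any new model.

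*The gain is uncertain, and differs for rank methods.* Nothing indicates the before–after correlation. At ρ = 0.2 ANCOVA gains less than 1 point over the one-year t-test. For linear ANCOVA the group effect and standard error are the same whether the outcome is change or the one-year value, but this does not carry over to ranks. In the lognormal setting, taking either version of rank-based ANCOVA gave 7.2 to 7.6% false positives at ρ 0.2 to 0.7. The lognormal example is also favourable to rank methods: in a simulation with an assumed floor (about 69% of controls at the floor at one year), Mann–Whitney gave 37/36/37% and rank-based ANCOVA 37/42/52%.

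All three limit the size of the point. None removes it: adjustment is nearly free, and the quantity is still unnamed.

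**Conclusion.** The point holds as a low-cost improvement to the secondary analysis, not as an error that invalidates it. Baseline values exist for POP-Q and ICIQ-VS, the planned group tests do not condition on them, and the tested quantity is not stated.

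Under the assumptions above, adjustment adds about 1, 11 and 27 points of power over a one-year t-test at ρ = 0.2, 0.5 and 0.7 (48.6 − 47.8, 58.7 − 47.8, 75.2 − 47.8). Over a change score with equal SDs it adds about 16, 11 and 6 points (48.6 − 32.5, 58.7 − 47.8, 75.2 − 69.1). Real gains depend on arm sizes, SDs, effects and correlations that the documents do not report.

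**What to change.** 1. For each score measured twice, state whether the one-year value or the change is compared. The change wording for POP-Q can stay if that is what is meant.
2. For approximately normal scores, add an ANCOVA of the one-year value on group and the woman's own preoperative value. Report the adjusted mean difference with its 95% CI.
3. For ordinal or skewed scores, where the plan uses Mann–Whitney, use rank-based ANCOVA or ordinal regression of the one-year value on group and baseline. Fix the outcome quantity, because rank-based results for change and for the one-year value can differ.
4. Assign each score to one of the two models in advance by its type, not by looking at its distribution.
5. Report the planned t and Mann–Whitney results alongside, saying which quantity they use.
6. Include UDI-6 and IIQ-7 only if preoperative scores exist.
7. Label the adjusted analysis post hoc for the 12-month report, since the opening of Materials and Methods already describes the first-year results of "two parallel groups, conducted in the tertiary referral training and research hospital, were evaluated". The listed visits are "one week, one month, three months, and one year post-surgery", so no later follow-up is described for which it could be pre-specified.

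Cost: some added text, one more model per score, the post hoc label, and under 1 point of power against the one-year t-test if the correlation is near zero. POP-Q and ICIQ-VS need no new data; for UDI-6 and IIQ-7 the records must be checked for preoperative scores.
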